#### **4.5.2 Alternatives**

There are no standard guidelines for therapy for patients with AML and MDS who are relapsed/refractory to HMA therapy. Therefore the alternatives to this clinical study include patients not participating. Patients may opt for no treatment, best supportive care (transfusions, treatment of infections etc.), hydroxyurea (a general myelosuppressive agent for palliative care), low dose subcutaneous cytarabine, another clinical trial that they are eligible for, or other alternatives after discussion with their treating physician.

### **5. INVESTIGATIONAL AGENT/DEVICE/PROCEDURE INFORMATION**

#### **5.1 Investigational Agent/Device/Procedure**

**Please refer to the investigator's brochure provided by Celator pharmaceuticals. We will review and summarize the investigational agent here.**

##### **5.1.1 Introduction**

CPX-351 is a liposomal formulation of a fixed combination of cytarabine and daunorubicin in a 5:1 molar ratio within a liposome. *In vitro* studies have shown that maintaining this fixed molar ratio maximizes antitumor efficacy in cell lines and animal models compared to conventional free drug treatment. The rationale for use in patients with AML and higher risk MDS, is that delivery of a fixed, maintained ratio of 5:1 of cytarabine: daunorubicin will enhance efficacy compared to treatment with conventional free drugs in the 7+3 regimen.

##### **5.1.2 Dosage Form, Route of Administration, and Dosage Regimen**

CPX-351 is a liposomal formulation of cytarabine and daunorubicin in a fixed molar ratio of 5:1, contained within the liposome. The liposomal membrane is composed of distearylphosphatidylcholine (DSPC), distearylphosphatidylglycerol (DSPG) and cholesterol in a 7:2:1 molar ratio. A copper based loading process is used to encapsulate daunorubicin. The size of these liposomes is approximately 100 nm and the drug is filtered through a 0.22 micromolar filter for sterilization. One unit of CPX-351 contains 1.0 mg cytarabine (+/- 10%) plus 0.44 mg daunorubicin (+/-10%).

CPX-351 is provided by Celator pharmaceuticals as a sterile, pyrogen free, purple lyophilized formulation in 50 mL glass, single use vials. Each vial contains 100 units of CPX-351. The lyophilized cake is reconstituted with sterile water for injection to obtain a homogenous dispersion at 5 units/mL (ex. 20 mL sterile water with 100 units of drug, with final concentration 5 units per mL). After dilution in either normal saline or dextrose injection to a final concentration of 0.10 units/ml to 1.32 units/ml, CPX-351 is infused over 90 minutes intravenously. CPX-351 will be administered through peripheral or central venous access, using an infusion pump or other means to ensure drug administered over appropriate time period.

The dosing regimen for induction course #1 will be CPX-351 65 units/m^2/day on Days 1, 3, and 5., with CPX-351 65 units/m^2/day on Days 1 and 3 for induction course #2 for patients requiring a second course of induction. The dosing regimen for consolidation courses will be 65 units/m^2/day on Days 1 and 3.

**Table 1:** Components of CPX-351 Liposome Injection  
(image from CPX-351 Investigator’s Brochure provided by Celator Pharmaceuticals)

Component	mw	Amount per Vial	Amount per unit
Cytarabine, USP/PhEur	243	100 mg	1.0 mg
Daunorubicin HCl USP/ PhEur (reported as the free base)	528	44 mg	0.44 mg
Distearoylphosphatidylcholine	790	454 mg	4.5 mg
Distearoylphosphatidylglycerol	801	132 mg	1.3 mg
Cholesterol, HP	387	32 mg	0.3 mg
Copper gluconate, USP	454	92 mg	0.9 mg
Triethanolamine, NF, PhEur	149	7 mg	0.07 mg
Sucrose, NF, PhEur	342	2054 mg	20.54 mg

### **5.1.3 Drug Preparation, Storage, and Stability**

The appropriate number of vials of CPX-351 based on patient’s body surface area (BSA) should be removed from the refrigerator and reconstituted with sterile water to obtain a homogenous dispersion of 5 units/mL, before further dilution. Further dilution can be completed with either sodium chloride or dextrose injection. CPX-351 can be diluted to a final concentration between 0.10 to 1.32 units/mL prior to administration. CPX-351 should not be heated. Aseptic technique should be maintained throughout its preparation given no preservative is present.

Infusion must be started within 4 hours of dilution. Solutions for administration should be prepared in glass bottles or NON-DEHP polypropylene or polyolefin bags. Per company recommendations, only DEHP-free administration sets such as those that are polyethylene-lined should be used. An in-line filter with CPX-351 should not be used. Unused material in vials should be discarded using proper technique for handling and disposal of antineoplastic agents.

CPX-351 liposome injection cartons should be stored refrigerated at 5 degrees Celsius +/- 3 degrees Celsius in an upright position until the vials are used. Each carton contains 2 clear glass, single vial use vials. Drug material released by the company will be periodically tested and monitored for acceptable product attributes. The current shelf-life of CPX-351 is 24 months from the date of manufacture. Drug that fails to comply with specifications will be removed.

### **5.1.4 Proposed Mechanism of action of Cytarabine, an active component of CPX-351**

Cytarabine (or cytosine arabinoside) is a traditional anti-metabolite chemotherapy agent used for a variety of leukemias and non-Hodgkin’s lymphomas. It is thought to work by interfering with DNA synthesis for its main anti-neoplastic activity, by affecting rapidly dividing cells that require significant DNA synthesis. Cytarabine is metabolized intracellularly into an active triphosphate form (cytosine arabinoside triphosphate). This metabolite is able to become incorporated into DNA, and may inhibit alpha-DNA polymerase and inhibit DNA repair through effects on beta-DNA polymerase.

### **5.1.5 Proposed Mechanism of action of Daunorubicin, an active component of CPX-351**

Daunorubicin is a traditional chemotherapy agent of the anthracycline family. The anthracycline family of chemotherapeutic agents are used to treat a wide variety of cancers including leukemias, non-Hodgkin lymphomas, genitourinary and breast cancer. Anthracyclines are thought to cause DNA damage by affecting topoisomerase II, leading to changes in DNA coiling/uncoiling, ligation/religation [20] ultimately affecting DNA and RNA synthesis. Anthracyclines may also cause reactive oxygen species generation.

### **5.1.6 Proposed Mechanism of Action of CPX-351**

Given that chemotherapy drug combinations may have synergistic, additive, or antagonistic effects based on the ratio of agents being used, but that their combinatorial effects are difficult to control *in vivo* because of the independent pharmacokinetics of conventional free drug cocktails, there has been considerable interest in developing liposomal drug delivery vehicles that allow control of drug ratio exposure via coordinated pharmacokinetics to try to improve therapy efficacy via prolonged maintenance of optimal drug ratios *in vivo*.

In the preclinical studies [15] various fixed ratio liposomal formulations of combined cytarabine and daunorubicin were tested in leukemia cell lines and murine models. *In vitro* cytotoxicity curves from various tumor cell lines analyzed for synergy showed that the 5:1 cytarabine:daunorubicin drug ratio (CPX-351) was the most synergistic (53% synergy, 33% antagonism, 13% additive). *In vivo* pharmacokinetics in a mouse model comparing free drug cocktail versus CPX-351, were significant for findings of a longer elimination half-life with CPX-351, with the maintenance of a ratio of cytarabine:daunorubicin of 5:1-9:1 for over 24 hours whereas free drug was noted to be rapidly removed from the circulation. The absolute plasma concentrations of both drugs were also higher in the CPX-351 group in this model, compared to administration of free drug cocktail. Interestingly, bone marrow samples in this model were also found to have higher drug concentrations when CPX-351 was used, in comparison to free drug combination. Finally, fixed drug ratio liposomal formulations ranging from 1:1 to 12:1 were evaluated in a P388 leukemia mouse model, with findings of the 5:1 drug ratio being most therapeutically active with findings of increased survival.

Thus the proposed mechanism of action for improved efficacy of CPX-351 compared to conventional free drug administration of cytarabine and daunorubicin includes: 1) the maintenance of a synergistic 5:1 molar ratio for periods > 24 hours after infusion because of the encapsulation of the drugs; 2) the drug liposome has also been found to be stable and able to circulate for more than 7 days after drug infusion; 3) an additional mechanism may be the accumulation of CPX-351 in the bone marrow, as shown in mouse models, and 4) the preferential uptake of CPX-351 within cytoplasm of leukemic cells [15].

### **5.1.7 Summaries of animal and clinical studies**

#### ***Summary of CPX-351 in Animal Studies***

In the P388 leukemia model, mice who received CPX-351 (5:1 ratio of cytarabine: daunorubicin) had a higher survival at Day 55 compared to mice who received other ratios (1:1, 3:1, 12:1). CPX-351 has been compared to free drug cocktail in the P388, L1210, WEHI-3B, CCRF-CEM and HL-60B murine models. CPX-351 has also been compared to individual liposomal formulations in the P388 and WEHI-3B murine models. In these models, CPX-351 was found to have improved anti-leukemic activity over free drug cocktail and individual liposomal formulations.

Pharmacokinetic studies of CPX-351 have additionally been done in rat and dog toxicokinetic studies, showing 3:1 – 7:1 ratio maintenance for 24 hours following administration. Total plasma drug concentrations were higher for extended time periods with CPX-351 compared to free drug administration.

In the bone marrow engrafting CCRF-CEM human leukemia xenograft model, CPX-351 was found to deliver higher amounts of cytarabine and daunorubicin compared to free drug cocktails. Prolonged drug exposure with maintenance near the 5:1 molar ratio was also found with CPX-351 on the order of days. Extended leukemia clearance and improved survival were noted in this model. Interestingly, the concentrations of cytarabine and daunorubicin were found to be higher in leukemic cells compared to normal bone marrow cells. The mechanism of action for this is thought to be preferential direct uptake of intact liposomes in leukemic cells.

Of note, toxicology studies were completed using single dose and repeated dose administrations of CPX-351 in the Beagle dog and Sprague-Dawley rat models. These studies helped to identify the starting dose of CPX-351 at 3 units/m^2 for the subsequent Phase I dose escalation study in humans.

### ***Summary of CPX-351 in Human Studies***

There have been three clinical trials with CPX-351 that have completed accrual. A complete analysis has been published for the initial phase I trial [16] and accrual has been completed for two phase II trials, with ongoing followup. Data available for these trials is summarized here with additional information available in the investigator's brochure.

#### **Phase I Study of CPX-351: CLTR0305-101**

In this initial phase I study, the primary goal was to establish the maximum tolerated dose (MTD) for CPX-351 for recommendations on dosing for further phase II studies.

Pharmacokinetic assessments of plasma samples were made at every dose level and patients were monitored for signs of antileukemic activity. An induction course with CPX-351 administered on days 1, 3, and 5 over 90 minute infusions was designed to mimic the 7 day drug exposure with conventional 7+3 treatment. Patients with relapsed/refractory AML, ALL, and high risk MDS were eligible for the study. There were 43 pts with AML, 3 pts with ALL, and 2 pts with MDS who were treated. The median age of patients was 62 with an age range of 23-81. The starting dose of CPX-351 was 3 units/m^2, and studied dose levels were 3 (1 patient), 6 (1 patient), 12 (2 patients), 24 (4 patients), 32 (4 patients), 43 (4 patients), 57 (3 patients), 76 (3 patients), 101 (6 patients), and 134 units/m^2 (6 patients). There were 34 patients who were studied in the dose escalation part of the study.

Dose limiting toxicities were observed at the 10th dose level of 134 u/m^2 (3 DLTs in 3 patients of 6), including congestive heart failure (CHF; 1 pt), hypertensive crises (1 pt) and persistent cytopenia past 56 days (1 patient; recovery occurred at day 112). The patient with the CHF episode had prior 369 mg/m^2 daunorubicin and a total of 556 mg/m^2 including CPX-351, and as a result, phase II studies have included a cap of 500 mg/m^2 on cumulative anthracycline dose after one induction course of CPX-351 and patients with significant pre-existing cardiac disease were excluded. Thus 101 units/m^2 was found to be the MTD. An additional 14 patients were subsequently added to the 101 units/m^2 cohort during the expansion phase of the study to obtain additional safety and potential efficacy data, for a total of 48 patients. Grade 3 and 4 Non-hematologic toxicities included mucositis (1 pt), vomiting (1 pt), skin rash (3 pts), CHF (2 pts), elevated bilirubin (1 pt), and elevated transaminases (2 pts). In terms of initial efficacy data, of the total 48 patients, there were

11 patients who experienced a response (AML- 9 CR, 1 CRp; ALL- 1 CR). 8 of the patients with AML with CR had prior cytarabine + anthracycline therapy, confirming anti-leukemic activity. Of the total patients with CR, 5 pts were  $\geq$  age 60. The median duration of remission was 6.9 months.

In terms of pharmacokinetic analysis, this phase I study assessed the concentrations of cytarabine, daunorubicin, uracil arabinoside, and daunorubicinol and found that they exhibited mono-exponential, first order elimination with minimal early phase distribution.

The day 1 single-dose and day 5 multiple-dose plasma cytarabine and daunorubicin showed linear pharmacokinetic characteristics ( $C_{max}$  and AUC (0-T)) and the 5:1 molar ratio of cytarabine to daunorubicin was maintained for up to 24 hours on days 1 and 5 at all dose levels.

CPX-351 was found to have a markedly prolonged mean half-life and greater drug exposure (AUC) for both cytarabine and daunorubicin, compared to expected mean half-life and AUC with conventional free drug; and measurable drug levels of cytarabine and daunorubicin were detected  $> 7$  days after last dose with CPX-351.

### **Phase II Study of CPX-351: CLTR0308-204**

Study 204 is a randomized, open label, multi-center phase II trial comparing CPX-351 to conventional 7+3 in older patients ages 60-75 with newly diagnosed AML (including both de novo AML and secondary AML). One hundred twenty-seven patients were randomized 2:1 to CPX-351 or 7+3. 126 patients were treated, 85 on CPX-351 and 41 on 7+3. The primary endpoint was rate of response (CR+CRi). Success was defined as achievement of a trend towards superior efficacy with a one sided p value of  $< 0.1$  with approximately 80% power. Secondary endpoints were overall survival, event-free survival, CR+CRi duration, leukemia-free after induction, safety and practicality of CPX-351 as consolidation therapy and the response rate of CPX-351 between de novo and secondary AML. At entry patients were stratified by age 60-69 vs. age 70-75, cytogenetics  $< 3$  or  $\geq 3$  cytogenetic abnormalities, and type of AML, de novo vs. secondary. High risk patients were  $\geq 70$  years of age, or had complex cytogenetics, or had secondary AML. Standard risk patients were age 60-69 and had non-complex cytogenetics ( $< 3$  abnormalities) and had de novo AML. After accrual was complete, [name] from the Moffitt Cancer Center, Tampa, FL, reviewed all of the cytogenetic reports and made the final cytogenetic group determination. Randomization and stratification were successful in balancing demographic and leukemia associated risk factors between the two study arms.

CPX-351 produced superior rates of leukemic-free state and response, with similar duration of remission. The improvement in response occurred predominately in the form of CRi (CR with incomplete hematologic recovery). The study met the primary endpoint with a response rate (CR+CRi) of 66.7% compared to 51.2% with a p-value of 0.0712 (single sided,  $p < 0.1$ ). Further analysis of response demonstrated consistent benefit for CPX-351 in response rate across every patient subgroup, including stratifications based on age, cytogenetic group, and presence of secondary leukemia. Kaplan-Meier (K-M) analysis after a minimum follow up of 1-year demonstrated non-significant improvements for CPX-351 for Event Free Survival (EFS) and Overall Survival (OS) in the overall population and the high risk strata. Overall survival and EFS in the secondary AML group did reach statistical significance favoring the CPX-351 arm ( $p=0.01$ , HR 0.40; and  $p=0.04$ , HR 0.51 respectively). Of the 33 patients in the CPX-351 arm who had secondary AML, 13/33 (39%) had prior HMA exposure and 16/33 (48%) had not. There were 19 patients in the 7+3 arm with secondary AML; 7 of them had prior HMA exposure. The response rate in patients receiving CPX-351 who had secondary AML and prior HMA exposure was 54% (7/13

responded with CR/CRi); in contrast, the response rate in patients receiving 7+3 who had secondary AML and prior HMA exposure was 29% (2/7 responded with CR/CRi).

Induction mortality was assessed at Day 30 and 60. A trend towards a lower rate of early mortality was observed for CPX-351 treated patients at 60 days (4/85, 4.7% vs. 6/41, 14.6%,  $p=0.053$ ), evidence that CPX-351 treatment is acceptably safe and that higher rates of leukemia clearance may assist in reducing the early death rate. CPX-351 treatment was associated with greater myelosuppression and more prolonged cytopenias, with a higher frequency of febrile neutropenia (63.5% vs. 51.2%), bacteremia (35.3% vs. 19.5%), fungal infections (15.4% vs 0%), and bleeding events, compared to 7+3. There were 4 deaths in the total CPX-351 group (1 from pneumonia, 3 from bleeding events; 1 fall in a thrombocytopenic patient; 1 intracranial hemorrhage; 1 respiratory tract hemorrhage). Thus a low threshold for platelet transfusions for critical thrombocytopenia is recommended. However the lower mortality rate of CPX-351 indicates the safety of CPX-351 despite the greater myelosuppression and its consequences. Given the reduced early mortality and OS advantage in secondary AML, a phase III study is currently underway, comparing CPX-351 vs 7+3 in secondary AML age 60-75.

### **Phase II Study of CPX-351: CLTR0308-205**

Study 205 is a randomized, open label phase II trial comparing CPX-351 (100 units/m^2 given on Day 1, 3, 5) with intensive salvage therapy in patients adult patients < 65 years of age with AML in first relapse. The trial accrued 125 patients with a 2:1 randomization to CPX-351 to CPX-351 versus investigator's choice of salvage therapy. The primary endpoint was survival at one year. Secondary endpoints were CR+CRi rate, remission duration, event-free survival and 30/60/90 day mortality. CPX-351 was able to increase the rate of CR+CRi rate 49% vs. 41%, and had comparable 60-day mortality 15% vs. 16%. After 1-year of follow up there were trends favoring CPX-351 for event free survival (HR=0.66,  $p=0.08$ ) and overall survival (HR=0.75,  $p=0.19$ ). In the subset analysis of patients with unfavorable risk group by the European Prognostic Index there was a significant improvement in overall survival (HR=0.55,  $p=0.02$ ). The proportion of CPX-351 versus control treated patients alive at 1-year was 37% vs. 30%, and the proportion of unfavorable risk patients alive at one year was 30% vs. 10%.

In summary, data from the Phase I and both randomized Phase II studies demonstrate consistent high level activity of CPX-351 in AML, with increases in leukemia-free state and clinical response (CR+CRi) compared to conventional therapy.

### **5.2 Availability**

Celator pharmaceuticals will be providing CPX-351. Letter of intent has been accepted by Celator pharmaceuticals for provision of the drug for this study.

#### **5.4 Agent Accountability**

The study pharmacist or designee must maintain records of the delivery of CPX-351 to the study site, the inventory at the site, the use by each patient, and the disposition of unused product. These records should include dates, quantities, lot numbers, expiration dates and patient identifications. Institutions should maintain records that document adequately that the patients were provided the doses specified by the protocol and reconcile all investigational product received from the Sponsor. Records of storage conditions (temperature logs) must be kept for the entire period that CPX-351 is maintained at the institution.

### **6. DOSE MODIFICATIONS**

#### **6.1 Dose Delays and Modification during Induction Therapy:**

- 6.1.1 No further study therapy will be given if a patient experiences grade 4 non-hematologic toxicity during induction #1, with the exception of febrile neutropenia/infection or constitutional symptoms or if there is recovery to grade  $\leq$  grade 2 within 14 days
- 6.1.2 If a subject experiences grade 3 or higher non-hematologic toxicity during induction #1 with the exception of febrile neutropenia/infection or constitutional symptoms, the dose of CPX-351 will be reduced by ~33% (to 43 units/m^2/day) for induction course #2 (if patient requires a second induction), if 6.1.1 is met.

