**\*Reduced doses may be given based on toxicities experienced during prior cycles**

**LIST OF ABBREVIATIONS AND DEFINITION OF TERMS**

ADL	Activities of daily living
AE	Adverse event
AML	Acute Myeloid Leukemia
BID	Twice daily
BSA	Body surface area
CBC	Complete blood count
CI	Confidence interval
C MAX	Maximum concentration of drug
CNS	Central nervous system
CRF	Case report/Record form
CR	Complete response
CTCAE	Common Terminology Criteria for Adverse Events
DLT	Dose Limiting Toxicity
DSMB	Data Safety Monitoring Board
ECG	Electrocardiogram
GI	Gastrointestinal
Hgb	Hemoglobin
HIV	Human Immunodeficiency Virus
HMA	Hypomethylation therapy
HPF	High-power field
HTN	Hypertension
IRB	Institutional Review Board
IV	Intravenous
LLN	Lower limit of normal
MDS	Myelodysplastic syndrome
OS	Overall survival
PLT	Platelet
PD	Progressive diseased
PFS	Progression free survival
PR	Partial response
QD	Once daily
RR	Response rate
SAE	Serious adverse event
SD	Stable disease
TTP	Time to progression
ULN	Upper limit of normal
UNK	Unknown
WBC	White blood cell
WHO	World Health Organization

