#### **6.2 Dose Modification during Consolidation Therapy**

- 6.2.1 If a dose reduction was required because of grade 3 or higher non-hematologic toxicity (except for febrile neutropenia/infection or constitutional symptoms) or if blood count recovery required > 56 days during induction therapy, the dose of CPX-351 during consolidation #1 will be reduced to 43 units/m^2/day.
- 6.1.3 If a subject experiences grade 3 or higher non-hematologic toxicity during consolidation #1 with the exception of febrile neutropenia/infection or constitutional symptoms or if blood count recovery required > 56 days during consolidation #1, the dose of CPX-351 will be reduced by 33% for consolidation #2 (that is, either 43 units/m^2/day X 2 doses or 30 units/m^2/day X 2 doses depending on dose used for consolidation #1).

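### The dose-modification rules in Sections 6.1 and 6.2 cannot be applied consistently as written

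*Combined protocol and SAP*

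**What the plan says.** Four places govern reduced doses.

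- **Section 6.1.1** is a stopping rule: "No further study therapy will be given if a patient experiences grade 4 non-hematologic toxicity during induction #1". It continues "with the exception of febrile neutropenia/infection or constitutional symptoms or if there is recovery to grade" 2 or lower within 14 days. So grade 4 toxicity ends study therapy unless it is of an excepted type or recovers in time.
- **Section 6.1.2** is a reduction rule: "If a subject experiences grade 3 or higher non-hematologic toxicity during induction #1", outside the same excepted types, "the dose of CPX-351 will be reduced by ~33" percent, to 43 units/m²/day, "for induction course #2 (if patient requires a second induction), if 6.1.1 is met".
- **Section 6.2** covers consolidation. Rule 6.2.1 lowers the consolidation 1 dose to 43 units/m²/day on either of two triggers: "If a dose reduction was required because of grade 3 or higher non-hematologic toxicity", with the same excepted types, "or if blood count recovery required > 56 days during induction therapy". The rule for consolidation 2 (numbered 6.1.3, although it stands in Section 6.2) is triggered by toxicity or slow count recovery in consolidation 1 itself and requires no earlier reduction.
- **The Dosing Scheme** lists reduced doses for induction 2 and both consolidations, with the footnote "Reduced doses may be given based on toxicities experienced during prior cycles".

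Section 4.1 sets 65 units/m²/day on Days 1 and 3 as the standard for induction 2 and for each consolidation. It sends patients in CR or CRi after one induction to consolidation without a second induction.

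**The concern.** A dose rule should give any two investigators the same dose for the same patient. Here three points leave it open.

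1. The condition in 6.1.2 points to a rule whose main content is that treatment ends. It does not say whether the stop or one of its exceptions has to be met.
2. The toxicity branch of 6.2.1 asks whether a reduction was required earlier. The only toxicity-based reduction before consolidation is the one for induction 2, so the branch appears to miss patients who had the toxicity but no reduction.
3. The footnote is permissive, while Section 6 is mandatory.

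Safety is a primary outcome (Section 10.1), and the study is described as fixed dose (Sections 2.4 and 4). If doses after toxicity depend on how each investigator reads Section 6, patients are handled inconsistently and the safety results mix different rules. Qualifying toxicity is foreseeable: in Study 204, grade 3 rash occurred in 7 of 85 CPX-351 patients (8.2%). Diarrhea, acute renal failure, syncope and hypoxia are each listed there among grade 3–5 events above 5% (Section 7.1). That was a different population on a higher dose, so these figures are only indicative.

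**Working it through.** **Step 1: the plan's own figure.** The inputs are the 65 and 43 units/m²/day in Section 6.1 and the Dosing Scheme. The reduction is 1 − 43/65 = 0.338, or 33.8%, which agrees with the stated figure of about 33%. Over the two doses of induction 2 this is 2 × 65 = 130 against 2 × 43 = 86 units/m².

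**Step 2: what has to be met in 6.1.2.** Take a patient who needs induction 2 and had non-hematologic toxicity in induction 1 outside the excepted types. There are three readings:

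- (a) the stop in 6.1.1 is triggered;
- (b) the recovery exception in 6.1.1 is satisfied;
- (c) the patient was simply not stopped by 6.1.1.

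| Grade in induction 1 | Recovered to grade 2 or lower within 14 days | Stopped by 6.1.1 | Reduced under (a) | Reduced under (b) | Reduced under (c) |
|---|---|---|---|---|---|
| 3 | yes | no | no | yes | yes |
| 3 | no | no | no | **no** | **yes** |
| 4 | yes | no | no | yes | yes |
| 4 | no | yes | yes, but no therapy is allowed | no | no |

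Under (a) the only patients reduced are those who may receive nothing, so 6.1.2 has no effect. Readings (b) and (c) agree except in the second row. There, (b) leaves the patient without a reduction rule, so the 65 units/m²/day of Section 4.1 is the only stated dose, while (c) gives 43.

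**Step 3: who the toxicity branch of 6.2.1 reaches.** The reduction in 6.1.2 responds to toxicity in induction 1 and takes effect in induction 2. Hence:

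| Patient reaching consolidation 1 | Earlier toxicity-based reduction possible? | Toxicity branch of 6.2.1, read literally |
|---|---|---|
| Grade 3 or higher in induction 1, then induction 2 | yes, subject to Step 2 | applies if the dose was reduced |
| Grade 3 or higher in induction 1, no induction 2 | no | does not apply |
| First grade 3 or higher toxicity in induction 2 | no | does not apply |

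For grade 4 in induction 1, these rows concern only patients whom 6.1.1 allows to continue. The count-recovery branch of 6.2.1 and the consolidation 2 rule are unaffected, because neither depends on an earlier reduction.

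**Step 4: how many patients.** The documents give no rate of second induction. If a fraction *s* of consolidation patients had induction 2, at least 1 − *s* cannot have had an earlier reduction: 80% at *s* = 0.20, 50% at *s* = 0.50 and 35% at *s* = 0.65. These values of *s* are assumptions. The result bounds who could not have been reduced. It is not the share affected, which also requires qualifying toxicity.

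**Step 5: optional or mandatory.** For the second and third rows of Step 3, the footnote allows a reduction on the strength of prior-cycle toxicity alone. Section 6.2.1, read literally, does not call for one. Where both provisions apply, the footnote permits what Section 6 requires.

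**The case against.** The strongest reply is that this is loose drafting which a sensible investigator would read correctly. Section 6.1.1 does more than end therapy: its exceptions let patients continue. If the condition in 6.1.2 means that the requirements for continuing are satisfied, the two rules are compatible. Reading (a) would leave the Dosing Scheme's reduced-dose row for induction 2 unused, so it is hardly what was meant. Likewise, 6.2.1 can be read loosely as covering toxicity of a kind that calls for a reduction. The Dosing Scheme also lists a reduced consolidation 1 dose without requiring an earlier one, so the omitted patients are not without any provision.

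Much of this stands. A reader might infer that the rules flatly contradict each other. The documents do not support that: 6.1.2 has an ambiguous cross-reference, and 6.2.1 has a gap in coverage that the footnote partly fills.

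The charitable reading does not settle the matter, however. Two charitable readings, (b) and (c), remain, and they give different doses for unrecovered grade 3 toxicity. The footnote fills the gap in 6.2.1 only by making optional what Section 6 otherwise makes mandatory. The consolidation 2 rule is tied directly to toxicity, so a different kind of trigger in 6.2.1 cannot be assumed to be a mere matter of phrasing.

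**Conclusion.** The point holds as an ambiguity, a coverage gap and a conflict between optional and mandatory wording. For induction 2, the two workable readings differ for one group only: grade 3 non-hematologic toxicity, outside the excepted types, not recovered within 14 days. The difference is 65 against 43 units/m²/day (33.8%). For consolidation 1, the same dose difference arises for patients with grade 3 or higher toxicity who had no earlier reduction, unless slow count recovery triggers the reduction anyway. This assumes 6.2.1 is applied literally and that, under reading (b), the standard dose remains where no reduction rule applies.

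Three further inferences are tempting but not supported:

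- **That most patients fall outside 6.2.1.** No second-induction rate is given, and the assumed values above put the bound on either side of one half.
- **That grade 3 patients face treatment or none.** Section 6.1.1 stops therapy for grade 4 only. For grade 3 the open question is the dose.
- **That the response results are affected generally.** Response is determined after up to two inductions (Sections 10.1.2 and 12.4.2), and consolidation dosing comes later. Only the induction 2 ambiguity could bear on CR/CRi, and only in the narrow group above.

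The sample size and the two-stage rule are not affected. The matter deserves correction because it bears on patient safety and on a primary safety outcome in a trial of 33 patients.

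**What to change.** Reconcile Sections 6.1.1, 6.1.2 and 6.2.1 with the Dosing Scheme footnote:

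1. In 6.1.2, replace the reference to 6.1.1 with the exact condition intended, so that grade 3 toxicity with and without recovery within 14 days each has a stated consequence.
2. In 6.2.1, state whether the trigger is the toxicity itself or a prior dose reduction. Say explicitly what applies to patients who go from induction 1 straight to consolidation, and to those whose first qualifying toxicity occurs in induction 2.
3. Use *may* or *will* consistently in the footnote and in Section 6. Correct the rule numbered 6.1.3 within Section 6.2 at the same time.

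Which rule and which dose are right is for the investigators to decide; none is proposed here. The cost is a wording amendment, with no change to the sample size or the analysis.
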